## 2.3. Study Design

## 2.4. Statistical Hypotheses / Statistical Analyses

This study is mainly descriptive with no formal inference associated with the study objectives. Nominal P-value may be provided as reference. 2-sided 95% confidence intervals will accompany all effect estimates.

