## 4. ANALYSIS POPULATIONS

**Table 2. Summary of Study Populations**

Population	Definition / Criteria	Analyses Evaluated
All Screened	
The All Screened Population will consist of all participants who sign the ICF to participate in the clinical trial.
 
Participants in this population will be used for screen failure summary.
	
 
• Study Population
 

Full	The Full Population will consist of all subjects (except subject PPD ) who are enrolled in the study and attend Visit 1, and not withdraw informed consent.	
 
• Study Population
 
• Disease Progression Analyses
 
• Phenotypic Analyses
 
• Treatment Pattern and Healthcare Resource Utilization/Cost
 
• Safety Analyses
 

Sub-cohort	Sub-cohort is a subset of Full population. Subjects who are enrolled in the Biomarker & Digital sub-cohort and who provided at least one additional sub-cohort assessment.	
 
• Study Population
 
• Disease Progression Analyses
 
• Phenotypic Analyses
 
• Treatment Pattern and Healthcare Resource Utilization/Cost
 
• HRCT analysis
 

HRU	HRU is a subset of Full population. The following sites are not feasible to capture data by HIS, thus the patients enrolled from the following sites will be excluded from HRU analysis: 238160, 238222, 237965, 237971, 238155.	
 
• Treatment Pattern and Healthcare Resource Utilization/Cost
 

[figure not shown]
\*: Subject PPD cannot be categorized into either of the study arms (COPD patients, Chronic Bronchitis patients or Healthy Control), thus excluded from the Full population.

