## 5.4. General Considerations in Statistical Analyses

Unless otherwise specified, continuous data will be summarized using descriptive statistics: n, mean, standard deviation (sd), median, minimum and maximum. Categorical data will be summarized as the number and percentage of participants in each category.

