### **6.1. Participant Disposition**

A summary of patient disposition, including screening status, reasons for screen failures and completers of each visit will be provided for the All Screened Population. In addition, the number of participants enrolled by site will be summarized by arm using the Full population.

A summary of the number of participants in each of the analysis set described will be provided.

A summary of study disposition including factors shown in study population schematic (Figure 1 and Figure 2, respectively) will be provided for Full and Sub-cohort Population, respectively.

Duration of study will be summarized by arm in Full Population and Sub-cohort Population in a same table, using mean(sd), median, Q1, Q3, min and max. For any participants, the duration of study is defined as the number of days from enrollment to study completion or study discontinuation, i.e.

$$\text{Duration} = \text{Date of Final Visit} - \text{Date of Visit 1} + 1$$

The “Final Visit” is defined as the last scheduled visit (including exacerbation visit), regardless of Outpatient visits.

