### **15.1. Adverse Events**

A listing will be provided for all study procedure related SAEs in Full Population.

Death and cause of death in Full Population will be summarized by arm. If no death case is reported, the table will be omitted.

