### 17.5.2. Study Population

Demographics	
Age	
• Age will be calculated based on the Visit 1.	
• Birth date will be imputed as follows:	
• Any subject with a missing day will have this imputed as day '15'.	
• Any subject with a missing date and month will have this imputed as '30JUN'.	
• Birth date will be presented in listings as 'YYYY'.	
Age categories are based on at screening and are defined as:	
• <65 years	
• ≥65 years	

Subject disposition	
Discontinuation from Study Treatment	
Not Applicable.	

Subject disposition
Discontinuation from Study Treatment
Discontinuation from Study

Censoring will be performed as follows:
 
 
• For subject that withdraws consent for disclosure of future information, any data collected prior to withdrawal will be retained and reported.
 
• For subject that withdraws consent for disclosure, the site may use any publicly information to determine vital status at the end of the study and this information would be included in the final analyses.
 
• If a subject withdraws from the study, he/she may request destruction of any samples taken and not tested, such request will be documented in study records.
 
• Subject that is unreachable and fails to come back for both Visit 3 and Visit 4 will be considered lost to follow-up. Data collected prior to missed visits will be retained and reported.
 

Smoking status

 
• Smoking status: Never smokers are defined as those with a lifetime exposure of <1 package/year in their life (excluding passive smoker). Ever smokers (current or former) are defined as those with a lifetime exposure of <math>\geq 10</math> package/year. Former smokers are those who have stopped smoking for at least 6 months. Current smokers are those who are currently smoking. Passive smokers are defined as those with the presence of smokers living in the same household, or co-workers smoking nearby while indoors
 
• Smoking status will be reassessed at each scheduled clinic visit evaluated by participants' self-report (e.g. never smoker, current smoker, former smoker).
 
• Smoking history including Pack-years of smoking: Number of pack years (number of cigarettes per day / 20) x number of years smoked, e.g., 10 packyears means 20 cigarettes per day for 10 years, or 10 cigarettes per day for 20 years)
 

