**Death**

Details of any patient deaths, including date of death, will be recorded in the CRF. Information will be obtained from the telephone interview and from medical records in HIS. Cause of death will be recorded if available. Data from publicly available source will be used if participant is not contactable at the end of the study.

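### Death, an Objective 1 endpoint, is planned only as a number and percentage by arm, with no follow-up-time basis and a population rule that drops consent withdrawers

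*SAP*

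**What the plan says.** Protocol section 4 and SAP 2.2 both list death among the main-cohort endpoints of Objective 1. SAP 17.5.2 (Death) has the date of death recorded. The sources are telephone interview and hospital records (HIS), and then: "Data from publicly available source will be used if participant is not contactable at the end of the study".

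The only analysis in the current SAP is in 15.1: "Death and cause of death in Full Population will be summarized by arm". The format comes from SAP 5.4: "Categorical data will be summarized as the number and percentage of participants in each category". SAP 2.4 adds that "2-sided 95% confidence intervals will accompany all effect estimates", but does not say whether a by-arm death percentage counts as one.

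SAP 6.1 summarises study duration by arm, separately from deaths. Its end point, the final visit, "is defined as the last scheduled visit (including exacerbation visit), regardless of Outpatient visits".

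On who is counted, SAP Table 2 limits the Full Population to participants "who are enrolled in the study and attend Visit 1, and not withdraw informed consent". Protocol 8.2 lets the sponsor keep data collected before consent for disclosure of future information is withdrawn. SAP 17.5.2 repeats this and allows the site to use public information "to determine vital status at the end of the study and this information would be included in the final analyses".

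**The concern.** A percentage of everyone enrolled treats a person followed for three months like one followed for thirty. Deaths after leaving are counted only if tracing finds them. By-arm mortality can then differ between GOLD grades because tracing differs, and the table would not show which it is.

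The SAP uses follow-up time for comparable outcomes. Exacerbations get a log-time offset (7.1), and hospital visits get total follow-up years and a crude rate (14.2). Death, with its date collected, gets neither.

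The population rule adds a second distortion. Withdrawing consent happens after baseline, and only the living can do it. Removing those people takes time alive out of the denominator, and also removes any later deaths among them that could be traced.

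**Working it through.** **Plan figures.** The documents give no death rate, event count or tracing rate. The 25% used below is the dropout allowance for FEV1 completers (Protocol 10.1.3): 525 / (1 − 0.25) = 700 per group, as Table 2 of the protocol states. It is not an estimate of unknown vital status and serves only as an upper case.

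**Assumptions.** True 30-month mortality M = 5%. A share d leaves, at a time spread evenly over T = 2.5 years. A share v of leavers is traced. The death rate after leaving is k times the rate before.

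**Crude percentage, k = 1.**
- Hazard h = −ln(0.95)/2.5 = 0.0205 per year.
- Mean probability of being alive at the leaving time = 0.05/0.0513 = 0.975, so 2.52% of leavers die before leaving and 5.00 − 2.52 = 2.48% after it.
- Relative shortfall = d(1 − v) × 2.48/5.00 = 0.496 d(1 − v).
- d = 25%, v = 0: −12.4% (4.4% shown instead of 5.0%). With v = 80%: −2.5% (4.9% shown).
- d = 10%: −5.0% (v = 0) and −1.0% (v = 80%).

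**Crude percentage, k = 2** (solved numerically with M held at 5%). d = 25%: −21.8% (v = 0) and −4.4% (v = 80%). d = 10%: −9.3% and −1.9%. Setting M to 1% or 10% moves these relative errors by less than one point.

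**Cross-check with a different loss model.** With a 2% yearly death rate and exponential loss, 25% untraced gives 4.24% against a true 4.88% (−13%), and 10% untraced gives 4.63% (−5%).

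**Size of the unknown group** at d = 25%: 0.25 × 0.975 = 24.4% of the arm if none are traced, and 4.9% if 80% are.

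**Consent exclusion** (a share w withdraws, k = 1): deaths/N = [5(1 − w) + 2.52w] / [(1 − w) + 0.0252w].
- w = 5%: 4.876/0.9513 = 5.13%, or +2.5%.
- w = 10%: 4.752/0.9025 = 5.27%, or +5.3%.

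This runs against the first distortion.

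**Does a time-based rate do better?** Relative error at d = 25%, v = 80%:

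| Measure | k = 1 | k = 2 |
|---|---|---|
| Crude percentage | −2.5% | −4.4% |
| Rate, everyone censored at last contact | 0% | −10.9% |
| Rate, traced deaths and traced survivors' time both counted | 0% | −2.0% |
| Rate, traced deaths counted, survivors' time not | +11.1% | +8.6% |

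The rate improves on the percentage in both cases only when confirmed-alive time is credited.

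**Sampling error for scale** (exact 95% intervals, assumed deaths).
- 35 of 700 (GOLD I): 3.5% to 6.9%, that is −30% to +38% relative.
- 10 of 100 (GOLD IV): 4.9% to 17.6%.
- 85 of 1,700 (all COPD): 4.0% to 6.1%, that is −20% to +23%.

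**The case against.** The study is descriptive with no formal inference, and Protocol 10.2.2 prescribes frequencies and percentages for discrete endpoints, keeping person-year rates for counts. No time-to-death analysis is promised anywhere. That stands. A reader might infer a protocol breach, or a broken promise of confidence intervals, and the documents support neither.

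A reader might also infer that untraced people will be counted as survivors. The documents do not settle this. SAP 17.4.2 lists N and n separately for categorical data and defers to sponsor display standards not in the file. Not naming an unknown category in 15.1 is, taken alone, missing detail.

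SAP 6.1 already shows duration and visit completion. This helps little, because duration stops at the last scheduled visit and omits time covered by calls, HIS or public sources.

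The consent condition affects every Full Population endpoint, and SAP 2.1 says the SAP's population definitions apply. Both are true. But SAP 2.1 does not mention the consent clause, and the conflict with SAP 17.5.2 is most direct for vital status.

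The strongest objection is that a person-year rate can be worse than the planned percentage, as the last row of the table shows. It stands, and it sets the conditions in the fix. Confirmed-alive dates may also be harder to obtain at five sites, of which SAP Table 2 says "The following sites are not feasible to capture data by HIS".

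**Conclusion.** The point holds as a modest, inexpensive improvement. Death lacks the time basis that the same SAP gives to exacerbations and hospital visits, and the Full Population wording conflicts with Protocol 8.2 and SAP 17.5.2.

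The crude percentage would be low by about 1% to 5% relative if most leavers are traced, and by about 5% to 22% if none are. The consent exclusion pushes upward by about 2.5% to 5%. Mortality, leaving, tracing, withdrawal and the post-leaving death rate are all assumed. At 5% mortality these errors are smaller than sampling error in each arm. Only the extreme untraced case reaches the width of the interval for pooled COPD.

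A reader might go further and conclude that by-GOLD mortality will be materially biased, or that a quarter of vital status will be unknown. The documents do not support this. The 25% concerns FEV1 completers, tracing may resolve most leavers, and the two distortions oppose each other with no by-arm split given, so the net direction is unknown.

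**What to change.** In SAP 15.1:

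1. For the death endpoint, include every enrolled participant who attended Visit 1 and can be assigned to an arm. Keep consent withdrawers up to withdrawal, plus vital status where Protocol 8.2 and SAP 17.5.2 allow.
2. Keep the number and percentage of all known deaths as the main result. Add Kaplan-Meier 30-month mortality or deaths per 100 person-years, with 95% CI by arm, counting time from Visit 1 to death or the date last known alive. Credit confirmed-alive time to traced survivors. Where no such date exists, censor at last contact and leave later-traced deaths out of that rate. Set this rule by tracing source and not person by person, because a traced death normally brings a date and a traced survivor may not. State that censoring is assumed non-informative.
3. Show vital status unknown at Month 30, by arm, in the same table.

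The cost is SAP wording, one derived last-known-alive date (weaker at the five sites without HIS capture) and one extra table.

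Intervals in small arms will be wide. Take 10 assumed deaths observed in 100 GOLD IV participants with 25% leaving evenly over time. Leaving alone reduces 250 person-years to 250 × 0.875 = 218.75. Time lost to the deaths themselves brings it to about 207, at a constant hazard of 0.0484 per year (0.0484 × 206.6 = 10.0). The rate is 10/207 = 4.8 per 100 person-years, exact 95% CI about 2.3 to 8.9.

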## 17. APPENDICES

### 17.1. Appendix 1: Protocol Deviation Management and Definitions for Per Protocol Population

Protocol deviations will be tracked by the study team throughout the conduct of the study in accordance with the PDMP. Important protocol deviations as identified in the PDMP will be summarized and listed.

#### 17.1.1. Exclusions from Per Protocol Population Analysis

This is an observational cohort study, any subjects with protocol deviations will not be removed from the study analyses. Per protocol population is not defined in this study.

### 17.2. Appendix 2: Schedule of Activities

#### 17.2.1. Protocol Defined Schedule of Events

Protocol Activity	Screen/Baseline	Study visit				EW	Exacerbation visit ( $\leq 2$ ) 
		V1	V2	V3	V4		
visit							
Study month	M0	M6	M18	M30			
window	+3 days	$\pm 28$ days	$\pm 28$ days	$\pm 28$ days			
Procedures							
Informed consent 	X	-	-	-	-	-	-
Demography	X	-	-	-	-	-	-
Medical history	X	-	-	-	-	-	-
Health and lifestyle information/Exposures	X	-	-	-	-	-	-
Inclusion/Exclusion Criteria	X	-	-	-	-	-	-
COPD and Exacerbation History 	X	-	-	-	-	-	-
Concurrent medications	X	X	X	X	X	-	-
Smoking status	X	X	X	X	X	-	-
Spirometry 	X	X	X	X	X	X	-
Reversibility Testing	X	-	-	-	-	-	-
Patient reported	mMRC	X	-	-	-	-	-
	SGRQ-C	X	-	-	-	-	-
Questionnaires	CAPTURE	X		X			
	CAT (on-site visit)	X	X	X	X	-	X

**CONFIDENTIAL**

Protocol Activity		Screen/Baseline	Study visit				
	CAT (Phone Call)	Trimonthly Phone Call 					
Healthcare resource utilization and cost		-	X	X	X	X	X
Assessments							
COPD exacerbation assessment (on site visit) 		-	X	X	X	X	X
COPD exacerbation assessment (Phone Call) 		Trimonthly Phone Call 					
COPD medication and treatment (on site visit) 		X	X	X	X	X	X
COPD medication and treatment (Phone Call) 		Trimonthly Phone Call 					
Death		-	X				
Serious Adverse Event assessment 			X	X	X	X	X
Lab							
Blood Draw for e.g. fibrinogen/HsCRP/Cell count		X	-	-	X	X	X
Sub-cohort only							
Lung HRCT scan 		X	-	-	X	X	X
Daily steps		X 	-	X 	-	-	-
Evening diary (EXACT plus additional questions)		X 	-	X 	-	-	-
Monthly CAT		X 	-	X 	-	-	-
Blood biomarkers (inclusive of serum sRAGE, CC16, IP-10, HbA1c)		X	-	-	X	X	X
Sputum cytology 		X	-	-	X	X	X
Sputum microbiome 		X	-	-	X	X	X

CAT=COPD assessment test, COPD=Chronic Obstructive Pulmonary Disease, HRCT=High-resolution computed tomography, EW=Early Withdrawal, EXACT=EXAcerbation of COPD Tool; SGRQ-C=St.George's Respiratory Questionnaire for COPD.

1. Exacerbation visits only apply to subjects included in the Biomarker & Digital sub-cohort. Moderate exacerbations are defined as COPD exacerbations that require either systemic corticosteroids (intramuscular (IM), intravenous, or oral) and/or antibiotics. Severe exacerbations are defined as COPD exacerbations requiring hospitalization or result in death.
2. Informed consent must be conducted at the screen visit prior to performing any study procedures.
3. For COPD participants only;
4. When a trimonthly telephone interview overlaps a clinical visit, the COPD exacerbation assessment, COPD medication and treatment questionnaires will be completed at the clinic visit.
5. Data collection of COPD exacerbation assessment, COPD medication and treatment is not required for the healthy control participants.
6. CT scan should only be performed at withdrawal visit if the last study CT performed was more than a year ago. Inspiratory and expiratory HRCT scans are required at Visit 1 and Visit 4, while only inspiratory scan will be conducted on exacerbation visit.
7. Pre-and post- bronchodilator values of spirometry test will be collected at each site visit.

8. Physical activity will be evaluated by daily steps as assessed by a wrist band dispensed at baseline. Participants are required to keep wearing the wrist band for 1 month from Visit 1 (baseline) and Visit 3
9. Daily digital EXACT measurement for 6 months from Visit 1 (baseline) and Visit 3
10. Monthly digital measurement from baseline for 6 months, and monthly digital measurement from V3 for 6 months
11. Sputum can be collected spontaneously or can be induced, as per investigator judgement. Sputum sampling should only be done if, in the opinion of the investigator, it is safe for the subject.
12. Only SAEs relating to the study procedures are collected.

## **17.3. Appendix 3: Assessment Windows**

### **17.3.1. Visit Based Assessments**

Nominal visits (scheduled visit) will be used for reporting and analysis.

Assessment windows for the scheduled study visits are as follows:

Full population:

- Baseline/Screen (+ 3 days)
- Visit 2 ( $\pm$  28 days)
- Visit 3 ( $\pm$  28 days)
- Visit 4 ( $\pm$  28 days)

In addition, COPD and chronic bronchitis participants will be contacted by phone on trimonthly basis within  $\pm$  7 days of the planned date to assess the CAT and to collect information on exacerbation rates and COPD medications; healthy controls will be contacted by phone on trimonthly basis within  $\pm$  7 days of the planned date to assess the CAT only.

## **17.4. Appendix 4: Data Display Standards & Handling Conventions**

### **17.4.1. Reporting Process**

Software
• The version 9.4 or later of SAS software will be used.
Analysis Datasets
• Analysis datasets will be created according to CDISC standards

- For creation of ADaM datasets (ADCM/ADAE), the same version of dictionary datasets will be implemented for conversion from SI to SDTM.

#### Generation of RTF Files

- Rich Text Format (RTF) files will be generated for the final reporting effort for use in writing the CSR.

### 17.4.2. Reporting Standards

Reporting Standards	
General	

 
The current GSK Integrated Data Standards Library (IDSL) will be applied for reporting, unless otherwise stated (IDSL Standards Location: https://spope.gsk.com/sites/IDSLLibrary/SitePages/Home.aspx):
 
4.03 to 4.23: General Principles
 
5.01 to 5.08: Principles Related to Data Listings
 
6.01 to 6.11: Principles Related to Summary Tables
 
7.01 to 7.13: Principles Related to Graphics
 
	
Formats	

 
GSK IDSL Statistical Principles (5.03 & 6.06.3) for decimal places (DP's) will be adopted for reporting of data based on the raw data collected, unless otherwise stated.
 
Numeric data will be reported at the precision collected on the eCRF.
 
The reported precision from non eCRF sources will follow the IDSL statistical principles but may be adjusted to a clinically interpretable number of DP's.
 
	
Planned and Actual Time	

 
Reporting for tables, figures and formal statistical analyses : 
 
Planned time will be used in figures, summaries, statistical analyses and calculation of any derived parameters, unless otherwise stated.
 
The impact of any major deviation from the planned assessment times and/or scheduled visit days on the analyses and interpretation of the results will be assessed as appropriate.
 
 
 
Reporting for Data Listings: 
 
Planned and actual time will be shown in listings.
 
Unscheduled or unplanned readings will be presented within the subject's listings.
 
Visits outside the protocol defined time-windows (i.e. recorded as protocol deviations) will be included in statistical analyses.
 
 
 
	
Unscheduled Visits	

 
Unscheduled visits will not be included in summary tables.
 
Unscheduled visits will not be included in figures.
 
All unscheduled visits will be included in listings.
 
	
Descriptive Summary Statistics	
Continuous Data	Refer to IDSL Statistical Principle 6.06.1

Reporting Standards	
Categorical Data	N, n, frequency, %
Graphical Displays	
• Refer to IDSL Statistical Principles 7.01 to 7.13.	

## 17.5. Appendix 5: Derived and Transformed Data

### 17.5.1. General

Multiple Measurements at One Analysis Time Point	
• Mean of the measurements will be calculated and used in any derivation of summary statistics but if listed, all data will be presented.	
Study Day	
• Calculated as the number of days from visit 1:	
• Ref Date = Missing → Study Day = Missing	
• Ref Date < Visit 1 → Study Day = Ref Date – Visit 1	
• Ref Date ≥ Visit 1 → Study Day = Ref Date – Visit 1 + 1	

### 17.5.2. Study Population

Demographics	
Age	
• Age will be calculated based on the Visit 1.	
• Birth date will be imputed as follows:	
• Any subject with a missing day will have this imputed as day '15'.	
• Any subject with a missing date and month will have this imputed as '30JUN'.	
• Birth date will be presented in listings as 'YYYY'.	
Age categories are based on at screening and are defined as:	
• <65 years	
• ≥65 years	

Subject disposition	
Discontinuation from Study Treatment	
Not Applicable.	

Subject disposition
Discontinuation from Study Treatment
Discontinuation from Study

Censoring will be performed as follows:
 
 
• For subject that withdraws consent for disclosure of future information, any data collected prior to withdrawal will be retained and reported.
 
• For subject that withdraws consent for disclosure, the site may use any publicly information to determine vital status at the end of the study and this information would be included in the final analyses.
 
• If a subject withdraws from the study, he/she may request destruction of any samples taken and not tested, such request will be documented in study records.
 
• Subject that is unreachable and fails to come back for both Visit 3 and Visit 4 will be considered lost to follow-up. Data collected prior to missed visits will be retained and reported.
 

Smoking status

 
• Smoking status: Never smokers are defined as those with a lifetime exposure of <1 package/year in their life (excluding passive smoker). Ever smokers (current or former) are defined as those with a lifetime exposure of <math>\geq 10</math> package/year. Former smokers are those who have stopped smoking for at least 6 months. Current smokers are those who are currently smoking. Passive smokers are defined as those with the presence of smokers living in the same household, or co-workers smoking nearby while indoors
 
• Smoking status will be reassessed at each scheduled clinic visit evaluated by participants' self-report (e.g. never smoker, current smoker, former smoker).
 
• Smoking history including Pack-years of smoking: Number of pack years (number of cigarettes per day / 20) x number of years smoked, e.g., 10 packyears means 20 cigarettes per day for 10 years, or 10 cigarettes per day for 20 years)
 

COPD Exacerbation History

 
• Individual exacerbations during the 12/24 months prior to Screening and during the study were to be collected on the eCRF by the investigator
 
• COPD exacerbations with onset date on or after the date of Screening will not be counted in the counts of number of exacerbations in the past year; all other exacerbations recorded on the eCRF will be included in the counts, even if onset/resolution dates were missing or earlier than the start of the exact 12 month period prior to Screening
 
• Number of COPD exacerbations reported in the past year prior to Screening will be summarised according to three categories: moderate COPD exacerbation, severe COPD exacerbation and moderate/severe COPD exacerbation.
 
• Moderate COPD exacerbations are defined as exacerbation that required treatment with oral/systemic corticosteroids and/or antibiotics (not involving hospitalisation).
 
• Severe COPD exacerbations are defined as exacerbations that required in-patient hospitalisation.
 

